3.9 Outcomes

3.9.1 Primary outcome

The primary outcome is a composite of any stroke or death within 30 days after enrollment or ischemic stroke in the territory of the qualifying artery from 30 days to 1 year after enrollment.

Ischemic stroke is defined as a new focal neurological deficit of sudden onset persisting for at least 24 hours and confirm by cerebral infarction on CT or MRI. Ischemic stroke are further classified as being either in or out of the territory of the qualifying artery. We regard ischemic stroke either in or out of the territory of the qualifying artery within 30 days after enrollment as a primary outcome, but beyond 30 days through 1 year, only ischemic stroke in the territory of the qualifying artery is considered as a primary outcome. We define symptomatic intracranial hemorrhage (sICH) as parenchymal, intraventricular, or subarachnoid hemorrhage identified on brain MRI or CT, which led to new emergence or worsening of neurological symptoms lasting more than 24 hours or a seizure. Death is categorized as vascular-related or non-vascular-related, and all-cause death is considered a primary outcome within 30 days.

Ischemic stroke and intracranial hemorrhage will be determined by core-lab assessment of imaging, and neurological assessment will be performed at the study site by independent neurologist certified in NIHSS, adjudication of outcomes will be done by an outcome adjudication committee.

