3.6.1 Endovascular recanalisation (ER)

For patients presenting with ICA or MCA M1 segment occlusion, ipsilateral cerebral hemodynamic compromise is rigorously evaluated through computed tomography perfusion (CTP) or magnetic resonance perfusion imaging prior to enrollment according to a previous study.³¹ Moreover, the non-contrast and perfusion scans are additionally transferred to the Rapid Processing of Perfusion and Diffusion (RAPID) system, providing analysis of perfusion source images with respect to the DEFUSE 3 criteria¹³.

All patients who are scheduled to undergo ER should receive dual antiplatelet therapy (aspirin 100 mg per day and clopidogrel 75 mg per day) for at least three days before the procedure.

All procedures are performed under general anesthesia by an experienced interventional neuroradiologist. After placement of sheath introducers, heparin is given intravenously to maintain the coagulation time between 200 and 300 s. The 6- or 8- French guiding catheter is located distal to the occluded artery as much as possible. Under the route map, the micro guidewire in combination with a microcatheter and the microcatheter are used to carefully pass through the occluded segment. Angiography with the microcatheter should confirm that the guidewire is in the true lumen. The exchange micro guidewire is then sent into the micro catheter, and the microcatheter is exchanged out. The balloon catheter is advanced smoothly into the occluded segment along the exchange micro guidewire. After the occluded segment is dilated with the balloon, angiography with a guiding catheter is performed. Stents are deployed in cases of residual severe stenosis, vascular dissection and failure to maintain forward flow (according to the judgment of the neuroradiologist to select the stent). If one stent cannot completely cover the lesion, multiple stents can be implanted. Successful recanalization was defined as achieving a modified Thrombolysis in Cerebral Infarction (mTICI)³² grade of 2b or higher, coupled with residual arterial stenosis less than 50% in immediate post-procedural DSA imaging..

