After the procedure, if there are no evidence of hemorrhagic complications on the head CT scan, dual antiplatelet therapy is systematically continued. Aspirin 100 mg per day must be used for the entire duration of follow-up, and clopidogrel 75 mg per day (or ticagrelor 90mg twice a day) must be used for 90 days after procedure. After 90 days, the decision to whether to continue clopidogrel therapy will be based on the patient's clinical condition and the investigator's assessment.

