5.1. Primary Outcome

The primary outcome is a composite of any stroke or death within 30 days after enrollment or ischemic stroke in the territory of the qualifying artery from 30 days to 1 year after enrollment.

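### The 30-day any-stroke-or-death window of the primary outcome starts at enrollment with no stated limit on the wait for ER, so procedural hemorrhage, out-of-territory stroke or death after a late ER can fall outside it; a procedure-anchored sensitivity analysis is needed

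*Protocol*

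**What the plan says.** Protocol 3.9.1 defines the primary outcome as a "composite of any stroke or death within 30 days after enrollment", or ischemic stroke in the qualifying territory from then to 1 year. SAP 5.1 uses the same origin: "The primary outcome is a composite of any stroke or death within 30 days after enrollment". The protocol is explicit about what drops out later: "beyond 30 days through 1 year, only ischemic stroke in the territory of the qualifying artery is considered as a primary outcome". On mortality, "all-cause death is considered a primary outcome within 30 days".

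Enrollment and procedure are separate dates. Protocol 3.6.1 asks for dual antiplatelet therapy "for at least three days before the procedure", and it counts the second antiplatelet agent from the procedure ("must be used for 90 days after procedure"), whereas section 3.6.2 counts the same period from enrollment. No section states a longest interval from enrollment to ER. Protocol 3.6 and SAP section 4 form the groups by treatment received. Neither document has a clause or a sensitivity analysis that starts the early window at the procedure.

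**The concern.** A 30-day any-stroke-or-death component is the part of this composite that can charge procedural harm against ER. The protocol's Background says that recanalization in the non-acute phase carries more procedural risk, and more symptomatic intracranial hemorrhage, than in the acute phase. If the clock starts at enrollment and the procedure comes later, part of the period at procedural risk is not observed for the three event types that stop counting at day 30.

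Take ER on day 32 followed by a fatal hemorrhage on day 35. Neither the hemorrhage nor the death is a primary event. The censoring rule in SAP 7.2 is written for any stroke and composite vascular events. If it also governs the primary outcome, this patient is censored at death as event-free. SAP 7.1 names a single primary efficacy variable, so the superiority claim rests on the outcome from which such events are missing.

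**Working it through.** **Inputs from the documents.** Early window: 30 days from enrollment (Protocol 3.9.1, SAP 5.1). Events that stop counting at day 30: hemorrhagic stroke, out-of-territory ischemic stroke, death (Protocol 3.9.1). Event that continues to 1 year: qualifying-territory ischemic stroke. Upper limit on the enrollment-to-ER interval: none stated. The documents contain no waiting times, procedural event rates or timing of procedural events, so there is no planned figure to reproduce. The risk shapes, rates and delay distributions below are assumptions.

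**Step 1: days covered.** With ER d days after enrollment, covered post-procedure days = max(0, 30 − d).

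**Step 2: share of risk left out.** Let F(t) be the cumulative risk of the three event types t days after the procedure. The share of 30-day post-procedure risk left out is L(d) = 1 − F(30 − d)/F(30). For uniform risk, F(t) = t/30 and L = d/30. For front-loaded risk with half-life h, F(t) = 1 − 2^(−t/h). Example with d = 21, h = 3: F(9) = 1 − 2^(−3) = 0.875; F(30) = 1 − 2^(−10) = 0.999; L = 1 − 0.875/0.999 = 0.124.

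| Wait d (days) | Days covered | h = 1 day | h = 3 days | h = 7 days | Uniform |
|---|---|---|---|---|---|
| 3 | 27 | 0% | 0.1% | 2% | 10% |
| 7 | 23 | 0% | 0.4% | 5% | 23% |
| 14 | 16 | 0% | 2% | 16% | 47% |
| 21 | 9 | 0.2% | 12% | 38% | 70% |
| 27 | 3 | 12.5% | 50% | 73% | 90% |
| 30 or more | 0 | 100% | 100% | 100% | 100% |

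**Step 3: averaged over waits.** Assume a wait of 3 days plus an exponential delay, and h = 3 days. Simulation gives:

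| Mean wait (days) | ER on or after day 30 | Risk left out |
|---|---|---|
| 7 | 0.1% | 1% |
| 10 | 2% | 5% |
| 17 | 14% | 21% |
| 24 | 28% | 35% |

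**Step 4: absolute size.** If a share s of ER patients is treated after day 30 and the procedural hemorrhage/death risk is r, the ER event rate is understated by s × r. With s = 10% and r = 3%: 0.3 percentage points. With s = 25% and r = 10%: 2.5 percentage points.

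**Step 5: direction.** Late planned ER removes events from the ER group, which favors ER. Late unplanned ER in a patient who stays in the medical group removes events from that group, which favors medical treatment. The documents give neither count.

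**The case against.** The strongest reply is that late ER is not what the documents depict. Table 1 puts the procedure columns between baseline and discharge, ahead of the 30-day visit. Protocol 3.10.1 has the enrollment mRS and NIHSS assessed at admission. Feasibility review is an inclusion criterion, and perfusion assessment for ICA and M1 occlusions comes before enrollment. All this points to ER in the index admission. It stands as evidence on likelihood, but it is not a rule: nothing excludes a later procedure.

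Second, a reader might take the three-day antiplatelet lead-in as proof of a wait after enrollment. The documents do not support that. They do not say that it starts at enrollment, and patients may enroll up to 90 days after their event, so some could already be on treatment.

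Third, a reader might infer that procedural harm goes unreported. It does not. One-year mortality, disabling stroke, composite vascular events (with any stroke), periprocedural symptomatic hemorrhage and death within 7 days are secondary outcomes. SAP 7.2 plans a Kaplan-Meier comparison of any stroke over follow-up, and the SAP's Safety Analyses section compares serious adverse events by group. A procedural ischemic stroke in the qualifying territory remains a primary event after day 30. What remains is narrower: no planned analysis rebuilds the primary composite from the procedure date.

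Fourth, a common enrollment origin gives both groups the same window, and a procedure-anchored one does not. That is a good reason to leave the primary definition alone, and it stands.

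**Conclusion.** The gap follows directly from the definition: for ER d days after enrollment, only max(0, 30 − d) post-procedure days count for hemorrhagic stroke, out-of-territory stroke and death. Its size cannot be found from the documents. From a 1-day half-life to uniform risk, the share left out spans 0–23% at 7 days, 0–47% at 14 days and 0.2–70% at 21 days; it is 100% from 30 days under any shape. If ER takes place within about two weeks and the risk half-life is 1 to 3 days, the loss is at most about 2%.

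A reader might infer that the plan is biased toward ER. The documents support that direction only for late planned ER; late unplanned ER in medical-group patients works the other way, and the net depends on unknown numbers of each. Nor do they show that the loss is large. The supportable conclusion is that the primary comparison can be affected, and that the plan contains nothing that would show whether it was.

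**What to change.** Keep the enrollment-anchored primary definition. Add to the Primary Efficacy Outcome section of the SAP (the first of its two sections numbered 7.5) a pre-specified sensitivity analysis. Its early component counts any stroke or death within 30 days after enrollment, or within 30 days after any ER of the qualifying artery, planned or unplanned, in either group. The later component stays as it is. Report it beside the primary result, together with the distribution of enrollment-to-ER times and the number of procedures after day 30, with planned and unplanned ER shown separately.

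The cost is a re-derivation: procedure times (Protocol 3.10.2) and start times of serious adverse events (Protocol 3.11.4) are already collected. The downside is unequal windows. A patient with ER on day 14, for example, would have 14 + 30 = 44 days of any-event exposure, against 30 for a patient without ER. For planned ER this works against ER; for unplanned ER it adds events to the medical group. Both versions should therefore be shown. The analysis needs to be entered before the outcome comparison is run; if that has already happened, it should be labeled post hoc.

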3.9.2 Secondary outcomes

Secondary outcomes as follows:

- Mortality within 1 year;
- Ischemic stroke outside the territory of the qualifying artery within 1 year;
- Disabling stroke within 1 year;
- TIA in the territory of the qualifying artery within 1 year;
- Unplanned revascularization (EC-IC bypass surgery or ER) of the qualifying artery within 1 year;
- Myocardial infarction within 1 year;
- Composite vascular events within 1 year;
- Quality of life assessment (EuroQol -Five-Dimensions [EQ-5D] scale questionnaire) at 1 year;
- mRS score at 1 year;
- Periprocedural outcomes;
- Restenosis or reocclusion (symptomatic or asymptomatic).

Disabling stroke is defined by any of the following: (1) an mRS score of 3 or more, (2) an increase of at least 1 point in the mRS score from prestroke baseline, (3) a score on the composite NIHSS of 7 or more, or (4) an increase of at least 4 points in the NIHSS score from pre-stroke baseline.

TIA is defined as duration of a focal or global neurological deficit <24 hours, any variable neuroimaging does not demonstrate a new hemorrhage or infarction.

Composite vascular events within 1 year included any stroke, myocardial infarction, and unplanned revascularization within 1 year.

Periprocedural outcomes are: (1) successful recanalization rate, (2) periprocedural complications: in-stent thrombosis, distal embolization, symptomatic intracranial hemorrhage, parenchymal hematoma type 2 (defined by the Heidelberg classification³⁴), arterial dissection, arterial perforation, (3) residual stenosis, (4) NIHSS score at 24-72 hours, (5) death within 7 days.

Restenosis is defined as >50% stenosis within or immediately adjacent (within 5 mm) of the treated segment and >20% absolute luminal loss, reocclusion is defined as total occlusion of the target artery segment.

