7.2 Data Handling Conventions

Premature withdrawal and missing data

If any subject withdraws prematurely from the study (prior to the final visit), they are required to complete the withdrawal visit in the case report form (CRF). The reasons for withdrawal will be presented in a summary table. For the purposes of summaries and analysis of clinic visit data, this visit will be assigned to the next scheduled clinic visit for that subject, regardless of whether the date falls within the next visit window.

Efforts will be undertaken at study sites to reduce the amount of missing data. For the primary efficacy outcome, multiple imputations in a model including strong prognostic variables will be used. Also, sensitivity analyses will be undertaken to explore the effect of missing data on the endpoint and test the robustness of the estimate. Ultimately, only patients who entirely completed the 1-year follow-up are included in the final analysis.

Event rates

The number of people and person-time of events should be recorded in detail and showing the event rate of each treatment group in summary statement.

The event rate for each treatment group will be calculated as: the sum of number of event for all the patients/the sum of number of treatment periods for all the patients.

Time to event analysis

Differences between treatments in the risk of any stroke (ischemic or haemorrhagic) event or composite vascular events during follow-up will be assessed using standard Kaplan-Meier time-to-event approaches. The time to the first event will be used in the model when there are multiple events of the same type. Patients will be considered censored at the time of study termination or death if there are no events occurred during the study.

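### A stroke or intracranial hemorrhage fatal before 24 hours meets neither event definition and is missed in periprocedural sICH, any stroke and composite vascular events

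*Protocol*

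**What the plan says.** Protocol 3.9.1 defines both clinical events partly by how long symptoms last. An ischemic stroke is a "new focal neurological deficit of sudden onset persisting for at least 24 hours and confirm by cerebral infarction on CT or MRI". Symptomatic intracranial hemorrhage (sICH) is bleeding seen on brain imaging "which led to new emergence or worsening of neurological symptoms lasting more than 24 hours or a seizure". Neither definition has an alternative for a patient who dies first. The SAP has no definitions of its own and refers the reader to Supplement 1.

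Death is treated differently from one endpoint to another:

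- Primary outcome, early period (Protocol 3.9.1): "all-cause death is considered a primary outcome within 30 days".
- Primary outcome, late period (Protocol 3.9.1): "beyond 30 days through 1 year, only ischemic stroke in the territory of the qualifying artery is considered as a primary outcome".
- Secondary composite (Protocol 3.9.2): "Composite vascular events within 1 year included any stroke, myocardial infarction, and unplanned revascularization within 1 year". Death is not a component.
- Censoring (SAP 7.2, time-to-event paragraph): "Patients will be considered censored at the time of study termination or death if there are no events occurred during the study". That paragraph is written for any stroke, of either type, and for composite vascular events.

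**The concern.** A duration threshold separates a stroke from a transient event. It works badly when the patient dies before the threshold is reached: the deficit never resolved, yet the duration condition is not met. The TIA definition in Protocol 3.9.2 does not pick up the case either, because it requires imaging without new bleeding or infarction. The event is left without a category.

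This matters most for ER. The protocol's own Background names susceptibility to symptomatic intracranial hemorrhage as a safety concern of non-acute recanalization. Perforation and dissection at the index treatment can occur only in patients who have the procedure. If the rapidly fatal events are mostly procedural, the omission lowers the ER group's sICH rate and removes more events from ER than from medical treatment in endpoints that do not count death. There, an ER patient who dies within hours of a hemorrhage could be analysed as event-free up to death, while a medical patient who survives a mild stroke is an event.

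**Working it through.** The documents give no sample size, event rate or event count, so there is no planned figure to reproduce. The check is a trace through the text, followed by arithmetic on assumed values.

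**Step 1. The case.** An infarct or hemorrhage confirmed on imaging, death before 24 hours, and no seizure if it is a hemorrhage.

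**Step 2. Where it is counted.**

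| Endpoint | Counted? | Basis |
|---|---|---|
| Primary, days 0-30 | Yes, as death | Protocol 3.9.1 |
| Primary, after day 30 (in-territory ischemic) | No | Death no longer counts; duration condition not met |
| Periprocedural sICH (ER group) | No | Duration condition not met |
| Any stroke; composite vascular events | No; censored at death | Protocol 3.9.2, SAP 7.2 |
| Disabling stroke | No | Death is mRS 6 (Appendix 1) and would pass the first limb, "Disabling stroke is defined by any of the following: (1) an mRS score of 3 or more", but only for an event already coded as a stroke |
| SAE total | Yes, as death | Protocol 3.11.4, SAP 5.3 |
| 7-day death; 1-year mortality | Yes | Protocol 3.9.2 |

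Two rows rest on inference. For hemorrhage, the any-stroke row assumes that hemorrhagic stroke is judged by the sICH definition; no separate definition is given. For the late primary period, censoring at death is inferred, because the SAP 7.2 sentence is not written for the primary outcome.

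**Step 3. Illustrative size. All inputs are assumed.**

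*Periprocedural sICH.* Coded rate = true rate × (1 − f), where f is the share fatal before 24 hours without a seizure.
- True 4%: f = 10% gives 4% × 0.90 = 3.6%; f = 40% gives 4% × 0.60 = 2.4%.
- True 8%: f = 10% gives 8% × 0.90 = 7.2%; f = 40% gives 8% × 0.60 = 4.8%.

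The relative loss equals f by construction, so these figures say nothing about how large f is.

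*Any stroke.* Assume 150 patients per arm and true 1-year risks of 12% (ER) and 15% (medical): 18 and 22.5 events, ratio 0.80. Coded ratio = 0.80 × (1 − s_ER)/(1 − s_med), where s is the share of strokes lost in each arm.
- s_ER = 5%, s_med = 5%: 0.9 and 1.1 events lost; ratio 0.80, unchanged.
- s_ER = 10%, s_med = 0: 1.8 lost in ER; 0.80 × 0.90 = 0.72.
- s_ER = 20%, s_med = 0: 3.6 lost in ER; 0.80 × 0.80 = 0.64.
- s_ER = 0, s_med = 5%: 1.1 lost in medical; 0.80/0.95 = 0.84.

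The direction depends on which arm has the larger share. Equal shares leave the ratio unbiased.

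*Primary outcome after day 30.* Events lost per 150 patients = 150 × late in-territory risk × share fatal before 24 hours.
- Low end: 150 × 0.04 × 0.02 = 0.12.
- High end: 150 × 0.12 × 0.10 = 1.8.

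In days 0-30 no primary event is lost, because the death counts.

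**The case against.** The strongest reply is that these patients do not vanish. A patient who dies hours after a vessel perforation is a primary event if within 30 days of enrollment, an SAE through death, a 7-day death and a 1-year death. Perforation is listed as a complication in its own right, and parenchymal hematoma type 2, if that pattern is present, carries no symptom-duration rule. The SAP's between-group safety test is on adverse and serious adverse events, where death is included. All of this stands. It rules out the reading, which a reader might infer, that early procedural deaths are missing from the safety record. It does not repair the sICH rate or the composite, which are reported on their own terms.

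Three further limits also stand:

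- A reader might conclude that severe strokes in general go uncounted. They do not: a severe stroke survived past 24 hours is coded, and an early-fatal hemorrhage with a seizure still qualifies as sICH.
- A reader might infer that ER is made to look safer than medical treatment on sICH. The protocol lists sICH as a periprocedural outcome, and the SAP analyses procedural complications within the ER group, so no between-group sICH comparison is specified.
- The outcome committee may code these cases sensibly. Its manual of operations is cited in Protocol 3.12 but was not available for this review. Nothing in the protocol or SAP tells it to do so, and two assessors applying 3.9.1 literally would both record no stroke.

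**Conclusion.** The point holds in a narrow form and is minor. By the wording of Protocol 3.9.1, an event fatal before 24 hours (for hemorrhage, without a seizure) is neither ischemic stroke nor sICH. It is missed in the ER group's periprocedural sICH rate, in any stroke and in composite vascular events, subject to the assumption about hemorrhagic stroke. A late, rapidly fatal in-territory ischemic stroke is also missed in the primary outcome; the assumed inputs put this at about 0 to 2 events per 150 patients.

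The undercount favors ER only to the extent that early-fatal events are procedural, an argument that gives no direction after day 30. The size cannot be derived from the documents. A statement that sICH is understated by 10-40% would merely restate an assumed share, and the ratio of 0.64 is an extreme of assumed inputs, not an estimate.

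One uncertainty cuts across all of this. SAP 7.2 also limits the final analysis to patients who completed 1-year follow-up. If a death counts as non-completion, these patients could be excluded instead of censored, and the protection described for days 0-30 would go with them. The documents do not settle this.

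**What to change.** In Protocol 3.9.1, end both definitions with a clause such as *or resulting in death before 24 hours*, applying where the outcome committee attributes the death to infarction or hemorrhage confirmed on imaging or at any available autopsy. Apply the same rule to hemorrhagic stroke wherever any stroke is counted, and carry it into the adjudication manual.

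In SAP 7.2, state that a fatal stroke is an event on its date of onset and not a censoring at death. State also that patients who die are not removed by the restriction to those who completed 1-year follow-up.

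The cost is one clause in each of two definitions, two sentences in the SAP and re-adjudication of a few cases. The reported sICH and composite rates may rise slightly. Days 0-30 of the primary outcome would gain or lose no patients from the definition change, since those deaths already count.
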